Assessments	Within 16 weeks of Registration	Prior to start of RT	During RT	Prior to Surgery (within 4 weeks of surgery)	Surgery	Surgery Follow-up (Within 4 weeks after surgery)	At 4 months (+/- 2 months) after Surgery and every 4 months (+/- 2 months) years 1 and 2
History/physical	X						X

Karnofsky PS	X			X			X
CBC with differential	X						
MRI - tumor site	X			X			X
CT Chest or PET CT	X			X			X
Pregnancy Test (if applicable)	X*						
Toxicity Evaluation		X	X	X		X	X
MSTS, FACT-L	X			X			X
Tissue Collection for Analysis	X				X		
Blood specimen for analysis	X						

Table 4: Study Parameters

*If applicable within 72 hours prior to CT simulation.

VIII. **Tissue/Specimen Submission**

- A. We will collect pretreatment diagnostic tissue and surgical specimens (1 formalin fixed paraffin embedded (FFPE) block) from patients who undergo biopsies to determine diagnosis for this research project, which is standard of care. Biopsy tissue will be sent for outside testing for RNA sequencing. The tissue will be stored on campus. The parameters to be reviewed are histologic, cell kinetic/proliferation, angiogenesis, and molecular markers have been and are under investigation. A number of biomarkers are under investigation by the Sarcoma group. These include SPARC, TYMS, RRM1, ENT1, ERCC1, TOP1, and TOP2A. These biomarkers will be assessed on biopsy and resection specimens for patients enrolled on the study. This assessment will be done in an ancillary study.
- B. Blood specimen (10 ml EDTA) will be collected at the time of lab draw (within 16 weeks of registration) for biomarker testing. Specimens will be stored on campus and sent out for cytokine analysis.

i. Process:

1. After collection, invert tube(s) multiple times to ensure adequate mixing of EDTA.
2. Centrifuge specimen(s) within one hour of collection in a standard clinical centrifuge at ~2500 RPM for 10 minutes at 4°C (preferred). If unable to process samples at 4°C then spinning at room temperature is acceptable if done within 2 hours of draw. If the interval between specimen collection and processing is anticipated to be more than one hour, keep specimen on ice until centrifuging is performed.
3. Carefully pipette and aliquot 0.5 ml plasma into as many cryovials as are necessary for the plasma collected (5 to 8) labeled with and case numbers, collection date/time, time point collected and clearly mark specimen as "plasma". Avoid pipetting up the buffy coat layer.
4. Place cryovials into biohazard bag and immediately freeze at -70 to -90°C.
5. Store frozen plasma until ready for testing.

IX. **Assessment of Safety, Dose Modifications and Dose Delays**

- A. This study will be reviewed by the Medical College of Wisconsin Cancer Center Data Safety Monitoring Committee (MCW CC DSMC). A summary of the MCW CC DSMC activities are as follows:
 - i. Review the clinical trial for data integrity and safety.

- ii. Review all unexpected grade 3, and all grade 4, and 5 adverse events, as well as any others requiring expedited reporting as defined in this protocol. (Grades 4 & 5 events must be reported to the DSMC within 5 calendar days of study staff's knowledge.) Review all DSM reports.
- iii. Sequential boundaries will be used to monitor the post-operative wound-complication rate. The accrual will be halted if excessive numbers of grade 3 or 4 (page 32) complications are seen, that is, if the number of complications is equal to or exceeds X out of N patients (X/N) with full follow-up (see below). This is a Pocock-type stopping boundary (Ivanova, et al. 2013) that yields the probability of crossing the boundary at most 5% when the complications rate is equal to 50% (O'Sullivan, et al. 2002).
- iv. Accrual will halt for protocol review if 6/6 (6 patients out of the first 6), then 7/7, 8/8, 9/10, 10/11, 11/13, 12/14, 13/16, 14/18, 15/19, 16/21, 17/22, 18/24, 19/26, 20/27, 21/29, 22/31, 23/32, 24/34, and 25/35 grade 3-4 treatment related AE's.
- v. Submit a summary of any recommendations related to study conduct.
- vi. Terminate the study if deemed unsafe for patients.
- B. A copy of the MCW Cancer Center Data and Safety Monitoring Plan and membership roster will be maintained in the study research file and updated as membership changes.
- C. The committee will review reports from the study PI twice annually (or more frequently if needed) and provide recommendations on trial continuation, suspension or termination as necessary.

X. **Subject Withdrawal Criteria**

- A. This Protocol is designed for 35 patients. Accrual will terminate early based on toxicity analysis. Patients may also withdraw at any point if they wish to not be on study.
- B. Criteria for early Closure
 - i. Greater than 2 patients who have any grade 4 or higher toxicity during radiation. If a patient has a grade 4 or higher toxicity, then they will be taken off the study, administered a lower dose per fraction per the treating physician, and the study will be closed. We do expect grade 3 skin toxicity (moist desquamation in areas other than skin folds), as many patients have tumors that extend to the surface of the skin and thus will need to be bloused to get the appropriate dose to these areas. Thus, moist desquamation often occurs.
 - ii. ≥60% of patients with post-operative wound complications.
 - iii. As mentioned above, patients may also withdraw at any point if they wish to not be on study.
- C. The research coordinator and PI will be notified of the withdrawal of a patient and the appropriate documentation will be made.
 - i. The IRB will be notified at the time of withdrawal.
- D. Subjects will not be replaced.
- E. Follow up and data collection for withdrawn subjects will terminate at the time of withdrawal.
- F. Dose Modification
 - i. If any grade 4 toxicity occurs, the dose will be modified based on the BED calculator above and the study will be closed.

XI. **Endpoint Assessment**

- A. Study Design:
 - i. This is a non-randomized Phase II pilot protocol to determine the feasibility, toxicity, and disease control (local control, overall and progression-free survival) using hypofractionated pre-operative radiation therapy in patients with primary localized STS.
- B. Primary Endpoint:

- i. The primary aim of this study is to assess local control. We expect local recurrence rates of <7%. Local and regional recurrence will be defined for each lesion per the treating physician(s). Local recurrence will be defined if the patient has evidence of disease on imaging (MRI or CT or PET CT) or physical exam.

C. Secondary Endpoint:

- i. The secondary objective of this study is to assess quality of life, toxicity (see iii), disease-free survival and overall survival. Disease-free survival is defined as the time from enrollment until documented disease-recurrence or death, whichever occurs first. Patients who are disease-free and alive at the time of analysis will be censored at the time of their last follow-up. Patients will be followed for disease-free survival for a minimum of 2 years.
- ii. Quality of life will be assessed via the FACT-L forms and given at the specified time points above.
- iii. Toxicity from pre-operative hypofractionated radiation therapy for STS. Based on historical data, we expect there will be minimal toxicity, both acute and long-term. Adverse event rates will be compared at specific times using the CTCAE v 4.0.
- iv. Changes in imaging with MRI (T2, T1 post contrast, DCE and DWI) as well as pathologic correlation (percent necrosis, fibrosis, viable cells and tumor biomarker expression will also be ascertained in this study.
- v. Measure cytokine and tumor gene expression and immune response to radiation therapy and correlate with pathologic and clinical response.

D. Endpoint Analysis:

- i. Crude rates of locoregional recurrences will be documented as well as the time to development of recurrence or relapse. Time of last follow-up or death will also be noted. This will allow us to calculate disease-free and overall survival rates. We will compare these results to an IRB approved database that exists on pre-operative radiation therapy using standard dose and fractionation at 2 Gy per fraction to 50 Gy.
 - 1. This IRB approved database is a retrospective database in which patients with Stage I-III STS of the extremity and superficial trunk were treated with pre-operative radiation therapy using conventional fractionation. Crude rates of locoregional control, disease-free and overall survival will be assessed in this dataset.
 - 2. The data in this database is acquired from all patients who were treated with preoperative RT for localized STS from 2000-2012. This is a retrospective database of the patients treated at Froedtert and the Medical College of Wisconsin
 - 3. The variables included in this database include age, KPS, gender, cardiovascular history, smoking history, disease histology, location of disease, grade, MRI measurements, RT dose and dates, dates of surgery, pathologic findings including size, %necrosis, fibrosis and viable cells, margin status, wound complications, local recurrence, distant recurrence, survival, date of consult and last follow-up, and disease status.

XII. Statistical Considerations

- A. The PRIMARY ENDPOINT of this study is to assess local control
- B. The SECONDARY ENDPOINTS are to assess toxicity, quality of life, disease-free survival and overall survival. Also, changes in imaging (MRI) and pathologic outcomes (biomarkers, percent necrosis, fibrosis and viable cells) will also be assessed.

XIII. Power Considerations for Local Recurrence (Primary Endpoints)

- A. The primary aim of a 2-year local recurrence rate of less than 3% will be evaluated by a one-sided equivalence test with an equivalence limit of 5% and a type I error rate of 10%. The study will conclude equivalence if the 2-year cumulative incidence of recurrence is less than 12% at the 0.10 type I error level. Power calculations are based on exact binomial probability calculations with an equivalence determined by no more than 12% local recurrence rate (within 5% of 7%), assuming a true 2-year local recurrence rate of 2.5%.
- B. If the true local recurrence rate is 12%, then with 35 patients the probability of observing a recurrence rate of 3.1% or less (≤ 1 of 35) is 8.97% (one-sided type I error = 0.0897).
- C. If the true local recurrence rate is 2.5%, then with 35 patients the probability of observing recurrence of 3.1% or less (≤ 1 out of 35) is 81.0% (Power).
- D. This is as close as we can get to a one-sided equivalence test with 10% type I error and 80% power with exact binomial calculations. The probability of falsely rejecting the null hypothesis (*hypofractionation treatment is worse than standard*) with only 0 or 1 recurrence out of 35 patients is less than 10% if the actual recurrence rate is 12% or more. There will be at least 80% power to reject this hypothesis if the true recurrence is 2.5% or less.

XIV. Considerations for Toxicity, QOL, Disease-Free Survival and Overall Survival (Secondary Endpoints)

- A. Overall survival and disease-free survival will be estimated using the product limit estimator and presented as Kaplan-Meier plots. Cumulative incidence rates will be calculated for local recurrence and adverse events. Quality of life data will be summarized for each time point, and compared using non-parametric statistical methods.
- B. Toxicity will be measured via the CTCAE v. 4.0 and the MSTS score. We will compare toxicity to the standard historical control for preoperative radiation therapy in STS (NCIC, O'Sullivan et. al) (5)
- C. Quality of Life will be measured with the FACT-L validated questionnaire.

XV. References

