Supporting Cytokine Analysis	Rutkowski, et al. 2002 (24)	Cytokine serum levels in soft tissue sarcoma patients: correlations with clinco-pathologic features and prognosis	Serum levels of some proinflammatory, hematopoietic and angiogenic cytokines and cytokine receptors are elevated, frequently in parallel, in a large percentage of soft tissue sarcoma patients. Significant correlations of serum cytokine levels with tumor size and grade suggest that some of these cytokines may be directly or indirectly involved in the progression of soft tissue sarcomas. Serum assays of IL-6, IL-8 and TNF RII before or after the treatment may be useful in establishing soft tissue sarcoma patients prognosis.

III. OBJECTIVES

- A. Hypothesis: We hypothesize that pre-operative hypofractionated radiation therapy for localized STS will result in local control and toxicity similar to conventional fractionation with less cost, more patient convenience and decreased overall treatment time.
- B. Objectives:
 - i. The primary objective of the study is to assess the local control, which will be assessed via physical exam and MRI.
 - ii. The secondary objectives are as follows:
 - 1. Assess toxicity, QOL using FACT-L
 - 2. Assess disease-free and overall survival using the product limit estimator and presented as Kaplan-Meier plots.
 - 3. Assess the acute and long term toxicity of hypofractionated pre-operative radiation for localized, stage I-III STS will be assessed via the CTCAE version 4.0 (Appendix III) and the Musculoskeletal Tumor Rating Scale (Appendix III).
 - 4. Assess radiologic changes due to hypofractionated radiation through the standard and advanced sequences of MRI
 - 5. Assess pathologic changes due to hypofractionated radiation through the expression of tumor biomarkers, percent necrosis, fibrosis and viable cells.

IV. ELIGIBILITY CRITERIA

- A. Inclusion Criteria
 - i. ≥ 18 years of age
 - ii. Biopsy obtained within 16 weeks prior to registration
 - iii. Pathologic confirmation of primary soft tissue sarcoma of the upper or lower extremity or chest wall. As per protocol per the STS tumor group, if biopsy was done at an outside hospital, then it will be reviewed by the pathologists at Froedtert and the Medical College of Wisconsin.
 - iv. Stage I-III Soft Tissue Sarcoma of the extremity or chest wall without evidence of metastatic disease (Appendix II)
 - v. Medically operable
 - vi. (History and Physical within 16 weeks of registration

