- i. Treatment interruptions should be minimized. More than a 2-week interruption (holidays and weekend are not included) will be considered a major violation.
- ii. Long term adverse effects will be measured 4 months after radiation for years 1 and 2

Table 3: Compliance Criteria

Per Protocol	90% of the PTV is covered with that prescription dose. No more than 10% of the PTV receives a dose that is >110% of the prescribed dose.
Minor Deviation	Greater than 10%, but no more than 20% of PTV receives ≥ 110% prescription dose. Exceeding normal tissue tolerances by >2.5%
Major Deviation	The minimum dose to any volume falls below 90% of the prescribed dose. Or, more than 20% of PTV receives ≥ 110% prescription dose. Dose to the normal tissue structure(s) is > 5%

H. Adverse Events

- i. PLACEMENT OF FLAP: Flap reconstruction and/or placement at the time of resection or soon after resection within 1 month does not constitute as a graded toxicity, as these surgeries are done to close the primary wound. Flaps are often needed as STS are large and the tissue defect caused by surgery is not able to be primarily closed. In this setting, this does not constitute as a wound complication as the flap is used for closure. Should a flap need to be placed because of a wound complication after primary resection and final closure (either primarily or with a flap), then this would constitute as a CTC AE v 4.0 Grade 4 toxicity.
- ii. Acute: Wound complications are expected to develop in about 30-40% of patients. Other common radiation adverse events include if applicable to site of lesion: fatigue, regional alopecia, diarrhea, skin erythema and desquamation within the treatment fields, and reduction in blood counts.

- iii. Long-term: Common long-term treatment adverse events include: lymphedema of the extremity receiving radiation and surgery, subcutaneous fibrosis, and joint stiffness. Much less common radiation adverse events include osteoradionecrosis and bony fracture in the radiation field. There also is a risk of cancer occurring in a previously irradiated field.
- iv. All AE's grade 3, 4 or 5 will be collected. AE's that are grade 1 or 2 will not be collected. AE's will be captured for up to 2 years post treatment, death, or initiation of a new therapy, whichever occurs first. Planned flaps are not considered an adverse event.
- v. Table 5: Criteria for Early Closure or Dose Modification.

Grade 4 Toxicity (per CTCAEv4.0)	

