- ii. Surgery type will be at discretion of surgeon. Pathology will evaluate the resected specimen and calculate the percent of necrotic (non-viable) tumor in the specimen. This is standard practice at most institutions is done for patients not on protocol. Pathology slides will be sent to the Wisconsin Diagnostic Laboratories ([name]). The designated pathologist reading the slides will be [name]
- iii. The patient's tissue will be stored at the MCW tissue bank. The patients will be consented for this prior to storing tissue.

M. Other Therapy

- i. Supportive Therapy
 - 1. All supportive therapy for optimal medical care will be given during the study period at the discretion of the attending physician(s).

VII. Post-Radiation and Surgery Follow-ups and Patient Assessments (Table 4)

- A. Surgery will be scheduled 4-8 weeks after completion of hypofractionation radiation therapy. After surgery, patients will be seen by the radiation oncologists or surgeons every 4 months (+/- 2 month) for years 1 and 2 from the end of surgery. The exact assessments for these follow-up appointments are listed in Table 3. A 2-year follow-up is standard in STS and then endpoints assessed are overall and disease-free survival, as well as local control, toxicity and QOL in sarcoma studies.
- B. Patients will be evaluated by a surgeon within 2 weeks (\pm 2 weeks) after surgery for evaluation of wound healing (this is standard practice).
- C. Patients will be seen 4 months (+/- 2 month) after surgery (with physical exam) and at this time repeat imaging with a CT chest and MRI of the extremity will be obtained (this is standard practice for patients not on protocol). Treatment after failure will be at the treating team's discretion and documented.
- D. Patient will be seen subsequently 4 months (+/- 2 months) afterwards with repeat imaging with a CT chest and MRI of the extremity for years 1 and 2. Anchor time points are from the end of surgery
- E. Quality of life forms (see Appendix IV) will be filled out pre-treatment and at each follow-up visit beginning at the 4 months (+/- 2 month) from surgery visit with imaging.
- F. Toxicity at all-time points will be assessed using the CTCAE version 4.0. This is the standard toxicity scoring system used in many protocols. QOL assessments will be made using the FACT-L questionnaire (Appendix IV).

Schedule of Events

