APPENDIX III

CTCAE 4.0 Toxicity Grading

Edema

Grade	Toxicity
1	5 - 10% inter-limb discrepancy in volume or circumference at point of greatest visible difference; swelling or obscuration of anatomic architecture on close inspection
2	>10 - 30% inter-limb discrepancy in volume or circumference at point of greatest visible difference; readily apparent obscuration of anatomic architecture; obliteration of skin folds; readily apparent deviation from normal anatomic contour; limiting instrumental ADL
3	>30% inter-limb discrepancy in volume; gross deviation from normal anatomic contour; limiting self care ADL
4	-
5	-

Definition: A disorder characterized by swelling due to excessive fluid accumulation in the upper or lower extremities.

Radiation Dermatitis

Grade	Toxicity
1	Faint erythema or dry desquamation
2	Moderate to brisk erythema; patchy moist desquamation, mostly confined to skin folds and creases; moderate edema
3	Moist desquamation in areas other than skin folds and creases; bleeding induced by minor trauma or abrasion
4	Life-threatening consequences; skin necrosis or ulceration of full thickness dermis; spontaneous bleeding from involved site; skin graft indicated
5	Death

Fibrosis

Grade	Toxicity
1	Mild induration, able to move skin parallel to plane (sliding) and perpendicular to skin (pinching up)
2	Moderate induration, able to slide skin, unable to pinch skin; limiting instrumental ADL
3	Severe induration; unable to slide or pinch skin; limiting joint or orifice movement (e.g. mouth, anus); limiting self care ADL
4	Generalized; associated with signs or symptoms of impaired breathing or feeding
5	Death

Post-operative Wound Complications

Grade	Toxicity
1	Incisional separation of <=25% of wound, no deeper than superficial fascia
2	Incisional separation >25% of wound; local care indicated
3	Hernia without evidence of strangulation; fascial disruption/dehiscence; primary wound closure or revision by operative intervention indicated
4	Hernia with evidence of strangulation; major reconstruction flap, grafting, resection, or amputation indicated
5	Death

Musculoskeletal Tumor Rating Scale-Upper Extremity

PAIN		FUNCTION	EMOTIONAL	HAND POSITIONING	MANUAL DEXTERITY	LIFTING ABILITY
5	No pain	No restriction	Enthused	Unlimited	Unlimited	Normal load
4	Intermediate	Intermediate	Intermediate	Intermediate	Intermediate	Intermediate
3	Modest/Non-disabling	Recreational restriction	Satisfied	Not above shoulder or no/Prosupination	Loss of fine movements	Limited

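### Section VI.H.iv excludes grade 1–2 adverse events for up to two years, while the long-term toxicity objective and visit assessments set no grade limit; read literally, grade 2 late fibrosis and limb edema go unrecorded

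*Combined protocol and SAP*

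**What the plan says.** Section VI.H.iv collects all adverse events of grades 3 to 5 and then states: "AE's that are grade 1 or 2 will not be collected". Capture runs to two years after treatment, death or the start of a new therapy, whichever is first, so the rule covers the period in which late effects appear.

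Other sections set no grade limit:

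- The third secondary objective (III.B.ii.3) is "Assess the acute and long term toxicity of hypofractionated pre-operative radiation for localized, stage I-III STS", by CTCAE v4.0 and the musculoskeletal tumor (MSTS) scale.
- VI.G.ii has long-term adverse effects measured in years 1 and 2.
- VII.F says "Toxicity at all-time points will be assessed using the CTCAE version 4.0".
- Table 4 has a row headed "Toxicity Evaluation", marked before and during radiation, before surgery, within 4 weeks after surgery, and at each 4-monthly visit.

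VI.H.iii lists the late effects to be expected: "Common long-term treatment adverse events include: lymphedema of the extremity receiving radiation and surgery, subcutaneous fibrosis, and joint stiffness". Appendix III prints grades 1 and 2 for edema and fibrosis. Grade 2 fibrosis reads "Moderate induration, able to slide skin, unable to pinch skin; limiting instrumental ADL", and the grade 2 edema entry ends "readily apparent deviation from normal anatomic contour; limiting instrumental ADL". Section XI.C.iii says "Based on historical data, we expect there will be minimal toxicity, both acute and long-term".

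**The concern.** A stated rule appears to discard data that a stated objective needs. The hypothesis in III.A is that toxicity will be similar to conventional fractionation. The dose rationale in the Introduction calculates a higher late-effect biological dose than conventional treatment and accepts it partly because late toxicity should be low. The late effects named as common are therefore a direct check on that reasoning.

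If only grade 3 or above is recorded, a low count could be taken as support for minimal late toxicity while patients with moderate, function-limiting fibrosis or edema go uncounted. Grades not recorded at a visit may not be reliably recoverable afterwards. MSTS does not fill the gap: it scores pain, function, emotional acceptance and limb use, with no fibrosis or edema item.

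**Working it through.** This is mainly a comparison of texts; the plan gives no figure for late toxicity in this trial to reproduce.

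**1. What can be recorded under VI.H.iv as written**

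- Fibrosis: Appendix III has grades 1 to 5, so grades 3, 4 and 5 are recorded.
- Limb edema: Appendix III leaves grades 4 and 5 blank, so only grade 3 is recorded.
- Joint stiffness: Appendix III prints no CTCAE grades for it, but the same rule applies.
- Post-operative wound complications: Appendix III has grades 1 to 5, so grades 1 and 2 are excluded here too. X.B.ii closes the study at 60% or more of patients with wound complications and gives no grade. The sequential boundary in IX.A.iii counts grades 3 and 4, so it is unaffected.

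**2. The dose rationale (Introduction)**

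With an alpha/beta of 5 and dose × (1 + dose per fraction / 5):

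- this trial: 35 × (1 + 7/5) = 84 Gy;
- conventional treatment: 50 × (1 + 2/5) = 70 Gy.

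Both match the protocol's figures.

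**3. The late figures the protocol quotes (Introduction)**

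- Canadian randomized trial, preoperative arm: fibrosis of grade 2 or above in 31% (reference 7).
- The 5 × 5 Gy series: late toxicity in 15%, mainly limb edema and fibrosis, with no grade stated (reference 11).

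Neither is restricted to grade 3 or above.

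**4. Illustrative size at N = 35 (X.A)**

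- Expected patients with fibrosis of grade 2 or above at a true 31%: 0.31 × 35 = 10.85, about 11.
- Exact (Clopper-Pearson) 95% interval for 11/35 = 31.4%: 16.9% to 49.3%. This is the precision available if grade 2 were recorded and all 35 were assessed.

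The share of these cases at grade 3 or above is not in the documents. Taking an assumed share s, the expected recordable count is 35 × 0.31 × s, and the chance of recording none is (1 − 0.31 × s)^35:

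| Assumed s | Expected recorded | Chance of none |
|---|---|---|
| 5% | 0.5 | 58% |
| 10% | 1.1 | 33% |
| 20% | 2.2 | 11% |
| 30% | 3.3 | 3% |

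The range shows how far the answer depends on s; it does not estimate the number lost.

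**The case against.** The best defense is that VI.H.iv governs adverse event reporting only, and that all grades are scored separately at visits. VI.G.ii, VII.F, the Table 4 row and the printed grade 1–2 definitions all fit that reading. It is a fair one, so a reader who infers that the protocol definitely confines late effects to grade 3 or above goes further than the text allows. But no section names a separate record, and the exclusion in VI.H.iv is explicit. Under either reading the sections need reconciling.

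A second defense is that collecting only grades 3 to 5 is a legitimate workload choice in a 35-patient single-arm pilot, where late toxicity is secondary and descriptive. That stands, and it limits the weight of the point. It does not remove the need to state the limit in the objective and the analysis.

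A reader might also infer that the planned historical comparison is invalid because the 31% is a grade 2 or higher rate. The documents do not support that. XIV.B cites reference 5, whereas the 31% comes from reference 7, a late-morbidity report on patients of the same trial. XIV.B does not name the 31% as its benchmark.

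Nor do the documents support reading the 11 patients above as the number lost, since some would be grade 3 or above and recorded. The interval also assumes all 35 are assessable, although capture can end at death or new therapy and data collection ends at withdrawal (X.E).

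**Conclusion.** The point holds as an unreconciled conflict with a real consequence under the literal reading: function-limiting grade 2 fibrosis and limb edema would go unrecorded, and the trial would have no late-fibrosis rate on the same footing as the 31% it quotes. About 11 of 35 patients would have grade 2 or higher fibrosis if the true rate were 31%; the number at grade 2 cannot be derived from the documents. Any comparison would be descriptive, given an interval as wide as 17% to 49%.

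The reach is limited. No primary-endpoint rule uses grade 2 late effects, and grade 3–5 events and MSTS are unaffected. It would be wrong to add that wound events as a whole are unaffected: grades 1 and 2 are excluded, and the X.B.ii criterion does not say which grades it counts. The change is worth making because it is cheap and serves a stated objective.

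**What to change.** In VI.H.iv, write: *Adverse events below grade 3 are not recorded, except that grade 2 fibrosis, limb edema and joint stiffness (CTCAE v4.0; Appendix III grades where given) are recorded at the pre-radiation toxicity evaluation and at each 4-monthly post-surgery toxicity evaluation in Table 4.* The pre-radiation reading allows limb discrepancy or stiffness already present to be told apart from a late effect.

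In XIV, report late effects of grade 2 or above descriptively, with exact 95% confidence intervals, among patients assessed at a stated visit. Use extremity patients only for edema, because its grades rest on inter-limb discrepancy. Do not set a grade 3 or higher rate against a grade 2 or higher historical rate.

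If grade 2 is not added, state in III.B.ii.3 and XIV.B that late CTCAE toxicity is limited to grade 3 or above. In either case, state whether VI.H.iv limits adverse event reporting or all toxicity recording, and reconcile it with VII.F and with the ungraded wound criterion in X.B.ii.

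Cost: one pre-radiation evaluation plus six 4-monthly ones (months 4, 8, 12, 16, 20 and 24) makes 7 per patient. At most 3 fields × 7 evaluations × 35 patients = 735 entries, with no new visits or tests.
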